7.5 Study Size

The study is descriptive, and there is no hypothesis testing. Up to 100 patients with VHL disease-associated RCC, CNS hemangioblastoma or pNET will be enrolled in the registry.

The target sample size for the primary effectiveness analysis includes approximately 40 eligible patients with VHL disease-associated RCC and approximately 40 patients with VHL disease-associated CNS hemangioblastoma requiring treatment. Enrollment will be closely monitored during the enrollment period and enrollment of patients with each VHL disease-associated tumor type (RCC and CNS hemangioblastoma) will be stopped once the target sample size for that tumor type is reached with overall recruitment into the registry stopped once the sample size requirement for both tumor types is met. Given the frequency of tumor reductive procedures in MK-6482-004 (8% of RCC patients and 6% of CNS hemangioblastoma patients, with surgery or locally directed therapy during a median follow-up of \sim 3 years)⁴, this target sample size provides greater than 90% probability of observing at least one RCC procedure or one CNS procedure during follow-up.

A target sample of 40 RCC patients in the registry, offers reasonable statistical precision for estimating the true population estimate with an upper limit of the 95% confidence bound below the point estimate of 29% of patients in a separate VHL disease-associated RCC natural history study⁵ having at least one tumor reductive procedure within 2 years of follow-up (Table 2). There is limited published data on the natural history of patients with VHL disease-associated CNS hemangioblastoma.

⁴ based on 01-Apr-2022 cutoff (preliminary analysis)

⁵ unpublished data from MSD study (EP05047.00)

PRODUCT: MK-6482	PROTOCOL/AMENDMENT VERSION NO.: 6482-026/3.0
REVOPS ID NO: NIS102327	CORE DRC APPROVAL DATE: 28-NOV-2023
EPIDEMIOLOGY NO. (PE STUDIES ONLY): EP05047.006	CRC PRC APPROVAL DATE: N/A

Table 295% CI for the Cumulative Incidence of Health Outcome of Interest (Exact
Confidence Interval; Clopper-Pearson Method; PASS 2021)

Assumed incidence for RCC surgery and/or locally directed therapy	40 patients	
	LL	UL
4%	0.3%	15.5%
6%	1.0%	18.3%
8%	1.8%	21.1%
10%	2.8%	23.7%

CI=confidence interval, LL=lower limit, UL=upper limit, PASS=Power Analysis & Sample Size, RCC=renal cell carcinoma

As one patient can have both VHL disease-associated RCC and CNS hemangioblastoma requiring treatment, each would contribute to the required sample size for that tumor type. If this were to occur, it would result in less than 80 patients included in the effectiveness analysis.

All patients treated with belzutifan will be included in the safety analysis.

7.6 Data Management

A data management plan specifying all functions, procedures, and specifications for data collection, retrieval, cleaning, and validation will be created before data collection begins. The study and data management team for the registry will follow standard operating procedures that define the processes and staff responsibilities for the collection, cleaning, control, and archiving of data entered in the data management system.

Data collection:

Data reported on the index date or subsequent follow-up visits will be captured by the site in CRFs with an EDC system. The EDC and electronic CRFs will be designed with structured and scientific and medical input from a multifunctional team including a medical monitor, epidemiologist, observational research and data management experts, as well as, statisticians. Baseline medical information and history will be abstracted by sites at study entry, and follow-up data collection will be conducted every 6 months throughout the study period. Data will be recorded in the electronic CRFs by personnel at each study site using standardized approaches.

Prior to deployment of the study-specific EDC database, user acceptance testing will be performed. All reported data from sites participating in the study will be entered via a secure web-based EDC study database. Site personnel will be provided with secure usernames and passwords to enter study data into the EDC system. All electronic CRFs should be

PRODUCT: MK-6482	PROTOCOL/AMENDMENT VERSION NO.: 6482-026/3.0
REVOPS ID NO: NIS102327	CORE DRC APPROVAL DATE: 28-NOV-2023
EPIDEMIOLOGY NO. (PE STUDIES ONLY): EP05047.006	CRC PRC APPROVAL DATE: N/A

completed by designated, trained personnel or the study coordinator, as appropriate. The electronic CRF should be reviewed, electronically signed, and dated by the investigator. All changes or corrections to the electronic CRFs will be documented in an audit trail and an adequate explanation will be required. All participating sites will only have access to the data entered by the individual site on their own enrolled patients through the EDC system.

Data cleaning and quality assurance:

High data quality standards will be maintained, with processes and procedures utilized to ensure that the data are as clean and accurate as possible when presented for analysis. To ensure quality of the data entered, two documents will be developed and included a part of the study documentation: a data dictionary and rules for data validation. Data quality will be enhanced through a series of programmed data quality checks in the electronic CRFs that automatically detect anomalous data and provide immediate feedback if critical data are missing, out-of-range, illogical or potentially erroneous. Queries are built to automatically run on the data that is stored in the EDC and will run on a regular cadence established between the MAH and the contract research organization. Other procedures are included in the EDC to ensure quality of the data that is entered and stored including automated queries for data cleaning. Regular query reports will be run allowing for the reconciliation of any inconsistencies or errors that are found during these processes. Standardized coding will be used for medical terms using the latest versions of MedDRA and WhoDrug dictionaries. All data will be stored on the secure RAVE cloud system or servers. Concurrent manual data review will be performed by study monitors based on parameters dictated by the plan. All modifications to the data will be recorded.

To ensure quality of the data entered in the system, structured general training on the protocol, electronic CRF and EDC will be provided to the study sites. In addition, sites will be given electronic data entry guidance on how to enter data and the expectations for which elements should be entered from the medical record. The electronic CRF data entry guidance will be available in both PDF and embedded within the EDC for sites to use as a guide when entering data to ensure all protocol required elements are captured if they are available. Study personnel will be provided reminders to the sites of data entry deadlines for each study participant so that data is entered into the electronic CRF in a timely manner.

For observational studies, it is accepted that data could be missing or incomplete per the physician records. Incomplete and missing electronic CRF data will be flagged and collected as part of ongoing data quality monitoring in the study. Where information is not available, trained personnel or the study coordinator who are completing the electronic CRFs will be able to click a checkbox which records these data as 'Not Available'. Clicking this checkbox will lock all related fields in the form, thus reducing the probability of missing queries. Incomplete and missing electronic CRF data not related to critical data items will be flagged as non-critical or queried as 'Not Available' or 'Unknown' in the electronic CRF.

PRODUCT: MK-6482	PROTOCOL/AMENDMENT VERSION NO.: 6482-026/3.0
REVOPS ID NO: NIS102327	CORE DRC APPROVAL DATE: 28-NOV-2023
EPIDEMIOLOGY NO. (PE STUDIES ONLY): EP05047.006	CRC PRC APPROVAL DATE: N/A

Patient-level data for all patients enrolled in the study will be provided proactively by participating sites and will be anonymized. During the study, the MAH or designee may make site visits to review protocol compliance, compare electronic CRFs and individual patient's medical records to ensure that the study is being conducted according to pertinent regulatory requirements. Checking of the electronic CRFs for completeness and clarity, and cross-checking with source documents, may be required to monitor the progress of the study. Moreover, regulatory authorities of certain countries, IRBs/ IECs, and/or the Sponsor's Clinical Quality Assurance Group may wish to carry out source data checks and/or on-site audit inspections. Direct access to source data will be required for these inspections and audits; they will be carried out given due consideration to data protection and medical confidentiality.

The principal investigator (PI) at each study site will be responsible for maintaining a delegation log. Only those who have been trained on the protocol, assigned as eligible to enter data by the PI, and those that have completed the electronic CRF/EDC training will have access and ability to enter data. No study members will be able to access the EDC without proper system training. Training will be performed at the site initiation visit, when a new member joins the study team, and when retraining is necessary due to a quality concern. A data entry coordinator will review the medical record and enter data according to the electronic CRF completion guidelines that are provided to the site.

Archiving:

Data archiving and retention will be in accordance with Article 12.2 of the implementation regulations (EU/520/2012) from the EU. Pharmacovigilance data and documents relating to individual authorized medicinal products will be retained if the product is authorized and for at least 10 years after the marketing authorization has ceased. However, the documents will be retained for a longer period where MAH, EU, or national law require.

7.7 Data Analysis

The information provided in this section may be subject to changes that will be indicated in the final statistical analysis plan (SAP) of this study. The SAP will be developed as a separate document and approved prior to database lock, containing a description of the planned statistical analysis in detail with tables, figures and listings (TFLs) templates.

7.7.1 General Consideration

All statistical analyses will be performed using Statistical Analysis System[®] (Cary, North Carolina version 9.4 or higher) unless otherwise stated. No formal statistical hypothesis testing will be performed, and all the analyses will be primarily descriptive in nature. When appropriate, and unless otherwise specified, 95% confidence intervals (CIs) will be displayed.

	3	31
PRODUCT: MK-6482	PROTOCOL/AMENDMENT VERSION NO.: 6482-026/3.0	
REVOPS ID NO: NIS102327	CORE DRC APPROVAL DATE: 28-NOV-2023	
EPIDEMIOLOGY NO. (PE STUDIES ONLY): EP05047.006	CRC PRC APPROVAL DATE: N/A	

A 95% exact binomial CI (based on Clopper and Pearson method) will be calculated for proportion outcomes (e.g., primary outcome proportion of patients who undergo surgery or locally directed therapy).

Descriptive statistics will include the number of available data, number of missing data and the following:

- Mean, standard deviation (SD), minimum, median, maximum, first and third quartiles and 95% CIs for means/medians.
- Counts and percentages of each category for categorical variables with 95% CIs.

Percentages will be based on the number of non-missing observations.

Missing data will not be replaced. Imputation rules will be detailed in the SAP, as appropriate (e.g., for incomplete dates).

7.7.2 Analysis Populations

Effectiveness population: All patients with RCC and/or CNS hemangioblastoma meeting inclusion/exclusion criteria and receiving at least one dose of belzutifan.

Safety population: All patients treated with at least one dose of belzutifan.

As the approved indication statement for belzutifan may differ between countries included in the study, subgroup analyses may be performed for countries with similiar indication statements if sufficient sample size warrants.

7.7.2.1 **Populations Analyzed**

All effectiveness analyses will be performed on the effectiveness population. Safety analyses will be performed on the safety population.

7.7.2.2 Patient Allocation and Reasons for Exclusion from the Analyses

The rules for the allocation of patients to each of the analysis populations will be defined and documented during a data review meeting held prior to database lock.

7.7.3 Statistical and Analytical Methods

See Section 7.7.1 for general consideration.

	32
PRODUCT: MK-6482	PROTOCOL/AMENDMENT VERSION NO.: 6482-026/3.0
REVOPS ID NO: NIS102327	CORE DRC APPROVAL DATE: 28-NOV-2023
EPIDEMIOLOGY NO. (PE STUDIES ONLY): EP05047.006	CRC PRC APPROVAL DATE: N/A

7.7.3.1 Demographic and Other Baseline Characteristics

Demographic and clinicopathological characteristics will be tabulated and reported using mean, SD, median, minimum, and maximum for continuous variables; numbers and percentages for each category will be provided for categorical variables.

7.7.3.2 Patient Disposition and Withdrawals

The number and percentages of patients in each population will be tabulated. The reasons for patient exclusions from each of the populations will also be tabulated. In addition, the number of patients who were treated and who died will be tabulated. Primary reasons for withdrawal from the study treatment will be tabulated.

Additionally, age (in years) and sex for patients approached but who do not consent to participate in the study and reason(s) for not participating may be collected and summarized separately if agreed by institutional review boards (IRBs)/independent ethics committee (IECs).

7.7.4 Primary Effectiveness Analysis

To analyze the primary effectiveness objective, number and the proportion of patients who undergo surgery or other tumor reductive procedures will be summarized descriptively along with associated 95% CI separately for VHL disease-associated RCC and VHL disease-associated CNS hemangioblastoma.

To contextualize and benchmark results from this single-arm post-authorization study of belzutifan, data on the number and proportion of patients who undergo surgery and/or locally directed therapy in the absence of systemic therapy will be used. This will include, but may not be limited to, estimates and findings from a recently completed natural history study (EP05047.001) of VHL RCC patients collected during routine clinical surveillance at the US National Cancer Institute, and results of a second natural history study planned for patients with VHL disease-associated CNS hemangioblastoma.

Further details will be included in the SAP.

7.7.5 Secondary Effectiveness Analysis

The analysis of secondary effectiveness objectives will be presented as follows:

Number and proportion of patients who develop metastatic disease (RCC only), number and proportion of patients with occurrence of new VHL disease-associated RCC, CNS hemangioblastoma, or other VHL disease-associated tumor type, and treatment patterns will be summarized descriptively using frequency of counts or descriptive statistics such as n, mean, 95% CI of the mean, SD, median, minimum, maximum separately for VHL disease-associated RCC and VHL disease-associated CNS hemangioblastoma.

PRODUCT: MK-6482	PROTOCOL/AMENDMENT VERSION NO.: 6482-026/3.0
REVOPS ID NO: NIS102327	CORE DRC APPROVAL DATE: 28-NOV-2023
EPIDEMIOLOGY NO. (PE STUDIES ONLY): EP05047.006	CRC PRC APPROVAL DATE: N/A

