6 RESEARCH QUESTIONS AND OBJECTIVES

The primary aim of this registry is to characterize the effectiveness of belzutifan for patients with VHL disease-associated RCC and/or CNS hemangioblastoma treated in real-world clinical practice. The primary effectiveness parameter includes tumor reductive procedures given the clinical importance of this parameter and association with subsequent morbidity and mortality of disease.

Secondary aims are to describe potential serious adverse events (SAEs), occurrence of new VHL disease-associated tumors or tumor type, and metastasis during belzutifan use and to evaluate treatment patterns among all new users of belzutifan.

6.1 **Primary Objective**

- 1. Among new users of belzutifan with VHL disease-associated RCC, to describe the proportion of patients who undergo at least one renal tumor reductive surgery (e.g., nephrectomy) or locally directed therapy (e.g., radiofrequency ablation).
- 2. Among new users of belzutifan with VHL disease-associated CNS hemangioblastoma, to describe the proportion of patients who undergo at least one CNS tumor reductive surgery (e.g., craniectomy) or locally directed therapy (e.g., radiation therapy).

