6.2 Secondary Objectives

- 1. Among all new users of belzutifan¹, to describe:
 - a. Proportion of patients with treatment emergent SAEs, including the nature of these events.
 - b. Treatment patterns including the:
 - i. Duration of therapy
 - ii. Proportion of patients who discontinued treatment, time to treatment discontinuation, and summary of reasons for discontinuation
 - iii. Proportion of patients who interrupted treatment, time to treatment interruption, duration of treatment interruption, and summary of reasons for treatment interruption
 - iv. Proportion of patients with dose reductions, and reason for dose reduction.
- 2. Among new users of belzutifan with VHL disease-associated RCC and, separately, VHL disease-associated CNS hemangioblastoma, to describe:
 - a. Proportion of patients who develop metastatic disease (for RCC only)
 - b. Proportion of patients with occurrence of new VHL disease-associated tumor or tumor type

¹ see Section 7.2.1. (Inclusion Criteria). Depending on the approved local label, this may include patients with VHL disease-associated RCC, CNS hemangioblastoma, or pNET.

PRODUCT: MK-6482	PROTOCOL/AMENDMENT VERSION NO.: 6482-026/3.0
REVOPS ID NO: NIS102327	CORE DRC APPROVAL DATE: 28-NOV-2023
EPIDEMIOLOGY NO. (PE STUDIES ONLY): EP05047.006	CRC PRC APPROVAL DATE: N/A

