7.3.2 Outcomes

The primary effectiveness outcome is the proportion of patients who undergo surgery or other tumor reductive procedure. Reason for surgery and tumor characteristics preceding surgery will also be collected.

The secondary effectiveness outcomes include:

1. Metastatic disease (RCC only)

	23
PROTOCOL/AMENDMENT VERSION NO.: 6482-026/3.0	
CORE DRC APPROVAL DATE: 28-NOV-2023	
CRC PRC APPROVAL DATE: N/A	
	PROTOCOL/AMENDMENT VERSION NO.: 6482-026/3.0 CORE DRC APPROVAL DATE: 28-NOV-2023 CRC PRC APPROVAL DATE: N/A

- 2. Treatment patterns (e.g., duration of use, proportion of patients who interrupt, reasons for interruption) will be evaluated using data captured on belzutifan treatment exposure.
- 3. Occurrence of new VHL disease-associated RCC, CNS hemangioblastoma, pNET or other VHL disease-associated tumor type (pheochromocytoma, paraganglioma, retinal hemangioblastoma, endolymphatic sac tumor)

During follow-up, data on all new tumor types and number of lesions will be collected and all VHL disease-associated procedures, anti-cancer medications, and concomitant medications will be collected. If available, best response to treatment per local radiology assessment for primary tumors will be also captured at the time of belzutifan discontinuation.

Safety outcomes will include SAEs (including fatal outcome) as well as the nature of these events.

Any herein described health outcomes, collected per the protocol, will be summarized as part of any interim analysis (if required) and in the final study report in addition to being reported in real-time as individual adverse events (AEs)/product quality complaints (PQCs) if the criteria in Section 9 are met. Refer to Section 9 for AE reporting requirements and procedures.

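### Treatment patterns are an objective for all new users, but Section 7.7.5 analyses them only in the RCC and CNS cohorts and names means and SDs for censored times

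*Protocol*

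**What the plan says.** **Objective.** The Protocol's Section 6 sets a secondary aim "to evaluate treatment patterns among all new users of belzutifan". Section 6.2 places treatment patterns under objective 1, for all new users. They include duration of therapy, time to interruption, and "Proportion of patients who discontinued treatment, time to treatment discontinuation, and summary of reasons for discontinuation". The footnote on who counts as a new user reads: "Depending on the approved local label, this may include patients with VHL disease-associated RCC, CNS hemangioblastoma, or pNET".

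**Analysis.** Section 7.3.2 lists treatment patterns second among the secondary effectiveness outcomes: "Treatment patterns (e.g., duration of use, proportion of patients who interrupt, reasons for interruption) will be evaluated using data captured on belzutifan treatment exposure". Section 7.7.2.1 states: "All effectiveness analyses will be performed on the effectiveness population". That population is defined in Section 7.7.2: "Effectiveness population: All patients with RCC and/or CNS hemangioblastoma meeting inclusion/exclusion criteria and receiving at least one dose of belzutifan". Section 7.1 also confines effectiveness analyses to RCC and/or CNS hemangioblastoma. Section 7.7.5 then says that "treatment patterns will be summarized descriptively using frequency of counts or descriptive statistics such as n, mean, 95% CI of the mean, SD, median", with minimum and maximum, and that this is done "separately for VHL disease-associated RCC and VHL disease-associated CNS hemangioblastoma".

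**Follow-up.** Section 7.1 plans at least 3 years per patient and, with enrollment over 2-3 years, at most 5-6 years.

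**The concern.** There are two problems.

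1. **Population.** The objective and its analysis cover different patients. An analyst who follows Section 7.7.5 produces two cohort summaries and no figure for the population named in objective 1b.

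2. **Statistics.** Patients still on belzutifan when observation ends have right-censored times. Section 7.7.5 names no method that allows for this. A mean with its CI and SD must either be taken over those who stopped, or count censored times as if they were complete. In both cases the result depends heavily on how long the registry ran, and a reader could take it for persistence on treatment.

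**Working it through.** **1. Population, section by section**

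- Sections 6 and 6.2: all new users, pNET allowed by the footnote.
- Section 7.3.2: treatment patterns are an effectiveness outcome.
- Sections 7.1, 7.7.2 and 7.7.2.1: effectiveness outcomes are analysed in RCC and/or CNS patients.
- Section 7.7.5: the summary is given for each of those two tumor types.
- Elsewhere: Section 7.7.3.2 tabulates reasons for withdrawal from treatment, and Section 7.7.6 covers SAEs. Neither gives duration of therapy, interruptions, dose reductions or time to discontinuation.

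So no section supplies the all-user result.

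*Who drops out.* Patients with neither RCC nor CNS hemangioblastoma. With 100 enrolled and 40 + 40 non-overlapping cohort patients, 100 − 40 − 40 = 20 would remain. This is an illustration, not a forecast: 100 is a ceiling, recruitment stops once both cohort targets are met, and there is no pNET quota.

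*Why adding the cohorts fails.* Sections 7.1 and 7.5 let one patient count in both. If k patients do, the two summaries cover 80 − k people while summing to 80. Overlap could be common: Section 5 reports CNS hemangioblastoma in 51 of the 61 pivotal-study patients, all of whom had RCC.

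**2. Statistics for censored times**

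The protocol gives no figure for time to discontinuation, so there is none to reproduce.

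Inputs from Section 7.1: end of follow-up C between 3 and 5 years (2-year enrollment) or 3 and 6 years (3-year enrollment). Assumptions, not in the protocol: constant discontinuation rate r, even enrollment (C uniform), no other loss.

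- True mean = 1/r.
- Proportion discontinued = 1 − E[exp(−rC)].
- Mean among discontinuers = 1/r − E[C·exp(−rC)] / (1 − E[exp(−rC)]).
- Mean with every time cut at end of follow-up = (1 − E[exp(−rC)]) / r.
- 3-year discontinuation probability = 1 − exp(−3r).

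Worked case, r = 0.20, C from 3 to 5 years:

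- E[exp(−rC)] = (e^−0.6 − e^−1.0)/(2 × 0.20) = 0.452, so the proportion discontinued is 0.548.
- E[C·exp(−rC)] = ½ × (40·e^−0.6 − 50·e^−1.0) = 1.779.
- Mean among discontinuers = 5 − 1.779/0.548 = 1.75 years.
- Mean of cut times = 0.548/0.20 = 2.74 years.

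A simulation of 2,000,000 patients per setting gives the table below (3-5 / 3-6 years of follow-up):

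| Rate per year | True mean (y) | Mean among discontinuers (y) | Mean, times cut at end (y) | Discontinued (%) | 3-year probability (%) |
|---|---|---|---|---|---|
| 0.01 | 100 | 2.03 / 2.31 | 3.92 / 4.40 | 3.9 / 4.4 | 3.0 |
| 0.05 | 20 | 1.97 / 2.23 | 3.62 / 4.02 | 18.1 / 20.1 | 13.9 |
| 0.10 | 10 | 1.89 / 2.14 | 3.29 / 3.60 | 32.9 / 36.0 | 25.9 |
| 0.20 | 5 | 1.75 / 1.94 | 2.74 / 2.94 | 54.8 / 58.7 | 45.1 |
| 0.50 | 2 | 1.37 / 1.46 | 1.72 / 1.77 | 85.9 / 88.5 | 77.7 |
| 1.00 | 1 | 0.92 / 0.94 | 0.98 / 0.98 | 97.8 / 98.4 | 95.0 |

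From 1% to 20% per year the discontinuers' mean moves by less than 0.4 years while the true mean falls twenty-fold. The 3-year probability, which a time-to-event analysis would estimate, rises from 3.0% to 45.1%.

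**The case against.** **On the population.** The loss may be small. On the literal definition in Section 7.7.2, a patient treated for pNET who also has RCC or CNS hemangioblastoma stays in. Section 5 puts pNET penetrance at 8-17%, against 60-84% for CNS hemangioblastoma and about 70% lifetime risk for RCC. Section 7.7.3.2 also tabulates reasons for stopping treatment without limiting the table to the two cohorts. This stands as a limit on size. It does not remove the contradiction, because objective 1b still has no all-user analysis.

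**On the statistics.** The list in Section 7.7.5 is open, and Section 7.7 says that the SAP may change it, so a Kaplan-Meier analysis is not excluded. Nor does the protocol say that the summary is limited to discontinuers. That reading is suggested only by Section 7.7.1, under which missing data are not replaced, since a patient who never stopped has no stop date. If all times are cut at end of follow-up instead, a median below 3 years is correct when everyone has the planned minimum follow-up. All of this stands and makes the second part the weaker one.

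**Readings to avoid.** A reader might infer that time to discontinuation will come out near 2 years whatever the true rate. It will not: the discontinuers' mean is about 1.4 years at 0.5 per year and 0.9 at 1.0 per year. A reader might also infer that the plan cannot tell slow from fast discontinuation. The proportion discontinued is planned too, and at 5%, 10% and 20% per year it is 20%, 36% and 59% with 3-6 years of follow-up.

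**Conclusion.** The population mismatch is a plain contradiction between Section 6.2 and Sections 7.3.2, 7.7.2.1 and 7.7.5, and it rests on no assumption. Its numerical size is unknown and possibly small. Its consequence is that one stated objective has no matching result, and none can be built from the two cohort columns. It leaves the primary analysis untouched.

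The point on statistics holds in a limited form. Mean, CI of the mean and SD are poor choices for duration of therapy and for time to discontinuation or interruption under 3 to 5-6 years of follow-up. The figure of about 1.75-2.3 years applies to means among discontinuers at 1-20% per year, under a constant rate and even enrollment. The protocol states neither the rate nor the restriction to discontinuers. It therefore shows what the named statistics can do, and is not a prediction of the study's result.

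**What to change.** 1. In Section 7.7.5, with a matching line in Section 7.7.2.1, state that objective 1b is analysed in all treated patients (the safety population of Section 7.7.2), with the RCC and CNS cohorts shown as subgroups. Objective 2 stays in the effectiveness population.

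2. In Section 7.7.5, name a Kaplan-Meier or cumulative-incidence estimate for duration of therapy and for time to discontinuation and interruption. Keep mean and SD for completed quantities, such as the length of resolved interruptions. The SAP can settle the detail, such as censoring dates and the handling of death.

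The cost is a few lines of text. No new data are needed, because Section 7.3.1 already captures treatment start, interruption, resumption and discontinuation.
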